Protocol Number: WQ21-2301

[name]'s Aortic Arch Reconstruction: A Multicenter, Prospective Study of the Novel WeFlow-Tribranch Unique Embedded Aortic Triple-branch Arch Stent Graft System (GENIUS Study)

Trial Medical Device Name: WeFlow-Tribranch embedded aortic Triple-branch arch Stent Graft system

Model Specification: Refer to the protocol for specification details

Trial Medical Device Regulatory Classification:

Class III medical device requiring clinical trial approval Yes ☐ No ☒

Protocol Version Number and Date: V1.0/20230830

Lead Unit: First Medical Center of The Chinese PLA General Hospital

Coordinating Investigator: [name]

Sponsor: Hangzhou Endonom Medtech Co., Ltd.

Confidential

This document is confidential. The contents of this document may not be disclosed to other parties by any person or entity without express written permission from Hangzhou Endonom Medtech Co., Ltd. The above restriction excludes subjects or their legal representatives who signed an informed consent form as well as discussions with governing bodies, independent ethics committees (IECs) or staff involved in the trial.

Trial Protocol Summary

Name of the Trial	[name]'s Aortic Arch Reconstruction: A Multicenter, Prospective Study of the Novel WeFlow-Tribranch Unique Embedded Aortic Triple-branch Arch Stent Graft System (GENIUS Study)
Sponsor	Hangzhou Endonom Medtech Co., Ltd.
Trial Objective	The purpose of this clinical trial is to evaluate the safety and efficacy of the WeFlow-Tribranch embedded aortic Triple-branch arch Stent Graft system developed and manufactured by Hangzhou Endonom Medtech Co.; Ltd. in the treatment of patients with aortic arch aneurysm
Trial Equipment	WeFlow-Tribranch embedded aortic Triple-branch arch Stent Graft system
Sample Size	Considering a dropout rate of 20%, the planned enrollment is 90 subjects.
Sample Size Calculation	

 

 

 

 

 

 

 

Follow-Up Period	After surgery, each subject will require 60 months of follow-up.
Patient Inclusion/ Exclusion Criteria	Inclusion Criteria 
 1. Patients aged 18 to 80 years old 2. Patients diagnosed with aortic arch lesions requiring intervention, including true aortic arch aneurysms, pseudo-aortic arch aneurysms, and ulcers involving the aortic arch. 3. Patients showing a suitable vascular condition, including: 
 • Ascending aorta length greater than 50 mm (from the aortic sinusoid junction to the proximal cardiac margin of the innominate artery). • Ascending aorta diameter ≥ 24 mm and ≤ 48 mm; • Proximal anchoring zone length ≥ 30 mm; • Innominate artery diameter ≤ 24 mm and ≥ 6 mm, length ≥ 20 mm ; • Suitable arterial access for endovascular interventional treatment ; 4. Patients able to understand the purpose of the trial, participate in the trial voluntarily with informed consent form signed by the subject

	
him/herself or his or her legal representative, and willing to complete follow-up visits as required under the protocol.
 
5. [REDACTED]
 
[REDACTED]
 
[REDACTED]
 
[REDACTED]
 
[REDACTED].
 
Exclusion Criteria
 
 1. Patients that have experienced systemic infection during past three months; 2. Neck surgery was performed within three months; 3. Previous endovascular interventional treatment involving the aortic arch was performed; 4. Infectious aortic disease、Takayasu arteritis, Marfan syndrome (or other connective tissue diseases); 5. Patients with severe stenosis, calcification, thrombosis or tortuosity; 6. Heart transplant patients; 7. Patients that have suffered MI or stroke during past three months; 8. Patients with Class IV heart function (NYHA classification); 9. Active peptic ulcers or upper gastrointestinal bleeding occurring within the previous three months; 10. Hematological abnormality, defined as follows: Leukopenia ($WBC < 3 \times 10^9/L$), acute anemia ($Hb < 90 \text{ g/L}$); thrombocytopenia ($PLT \text{ count} < 50 \times 10^9/L$), history of bleeding or coagulopathy; 11. Patients with renal insufficiency, serum creatinine $> 150 \mu\text{mol/L}$, and/or end-stage renal disease requiring renal dialysis; 12. Patients that are pregnant or breastfeeding; 13. Patients with allergies to contrast agents; 14. Patients with a life expectancy of less than 12 months; 15. Patients currently participating in other drug or device research; 16. Any other disease or abnormality that the investigators believe may hinder endovascular interventional treatment.
--	--

Primary Endpoints	Rate of all-cause mortality and major stroke within 12 months after surgery. All-cause mortality includes cardiac mortality, non-cardiac mortality and mortality from unknown causes. Major stroke is defined as a modified Rankin score (mRS) ≥ 2 at 90 days following stroke onset (see Annex 2).
Secondary Efficacy Endpoints	
 1. Rate of immediate technical success following surgery. Immediate technical success is defined as successful delivery of the aortic and branching stent graft conveyors to their predetermined positions, accurate positioning and successful deployment of the stent, safe removal of the delivery device outside the body, and the absence of Type I and III endoleaks per imaging studies conducted at the end of the procedure with all branching stents patency. 2. Rate of aortic aneurysm progression under control. Maximum increase in the diameter of the aortic aneurysm was ≤ 5 mm when compared with preoperative aortic aneurysm as of a 12-month postoperative CTA review. 3. Incidence of Type I or Type III endoleak. Intraoperative, 1-month, 6-month, and 12-month DSA or CTA imaging studies showing endoleaks. Intraoperative endoleaks subject to adjuvant treatment are not recorded. Endoleaks occurring after the completion of the procedure followed by one or more endoleaks occurring in the same subject at different follow-up stages that were not treated are counted as a single instance. 4. Incidence of aortic covered stent graft displacement. CTA examination will be performed at 1, 6, and 12 months post operation to determine if the stent has migrated, and evaluations will be recorded for both the main and branch stents. Displacement is defined as a displacement of more than 10 mm in the aortic and branch stent grafts at follow-up time points compared with the 30-day postoperative reference imaging. 5. Postoperative branch vessel patency rate. CTA examinations will be performed at 1, 6, and 12 months post-operation to evaluate branch vessel reconstruction and assess for occlusion, stenosis, or in-stent thrombosis.
Secondary Safety Endpoints	
 1. Rate of conversion to thoracotomy or secondary intervention. Whether subjects require conversion to open thoracic surgery or secondary interventional procedures due to new-onset aortic dissection caused by

	
the index procedure.
 
 2. Rate of major adverse events occurring within 30 days after surgery. Refers to all-cause mortality, myocardial infarction, ischemic stroke or respiratory failure occurring within 30 days after surgery. More specifically, myocardial infarction refers to a drastic reduction or complete interruption of the coronary blood supply due to coronary artery disease, resulting in severe and prolonged acute ischemia of the corresponding myocardium, leading to necrosis of cardiomyocytes. Ischemic stroke refers to the end result of necrosis of brain tissue caused by narrowing or occlusion of the arteries supplying blood to the brain or insufficient blood supply to the brain. Respiratory failure is defined as a state resulting in significantly prolonged intubation, tracheotomy, deterioration of lung function, or other fatal outcomes. 3. Rate of aortic aneurysm-related mortality at 12 months post operation. Refers to mortality caused by a ruptured aortic aneurysm or endovascular interventional treatment. 4. Incidence of severe adverse events. Refers to an event that occurs during the clinical trial that results in mortality or serious deterioration in patient health, including a fatal illness or injury, a permanent defect in body structure or body function, or an event that requires medical or surgical intervention to avoid one or more permanent defects in body structure or body function. 5. Incidence of device-related adverse events. Device-related adverse events refer to an adverse medical event related to the use of a device that occurs during the course of the clinical trial. However, a distinction should be made with respect to normal postoperative stress response, such as fever and chest and back discomfort, which, in the judgment of the investigator, need not be recorded as an adverse event. Recording of device-related adverse events will be applicable for conditions that are deemed by the investigator to be definitely related, possibly related, or of indeterminate relationship, to the test device.
Trial Visitation Plan	
 ➤ Visit 1: Screening period (Day -15 to 0) ➤ Visit 2: Day of Surgery (Intraoperatively, after completion of stent-graft deployment) (Day 0)

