Globally, research on multi-branched stent grafts remains in the early stage. For instance, the NEXUS aortic stent graft system by Endospa adopts a modular design for thoracic aortic lesions involving the aortic arch; however, it only reconstructs the brachiocephalic trunk, while the left common carotid artery and left subclavian artery require two additional bypass procedures to maintain cerebral perfusion. Further studies are needed to verify whether the single arterial diameter can fully satisfy perfusion demands of all arch vessels¹⁹. This device has obtained CE (Conformité Européenne) certification and is currently undergoing pivotal clinical investigations under the FDA (Food and Drug Administration) regulatory framework. The Multi-branch dual in-branched stent graft by COOK¹³, the A-Branch triple in-branched stent graft system²⁰, and the RelayBranch stent graft by Terumo are also under feasibility evaluations^{7, 10, 21–23}. Notably, RelayBranch received FDA Breakthrough Device Designation in March 2022; nevertheless, stroke risk remains a critical concern for such products.

Addressing the current limitations of clinical endovascular arch repair techniques and devices, the Modular Integrated Triple-Branched Aortic Arch Stent Graft System investigated in this study integrates in-branch and modular design concepts. The system consists of an integrated ascending aortic stent graft subsystem, an integrated arch stent graft subsystem, branched stent graft subsystems, and aortic extension stent graft subsystems. The integrated ascending aortic stent graft features two built-in branches for endovascular reconstruction of the innominate artery and left common carotid artery via matched branched subsystems, while the integrated arch stent graft reconstructs the left subclavian artery and connects with the ascending module to treat combined arch and descending aortic lesions, achieving total endovascular repair without debranching surgery. The modular integrated vascular design maintains uninterrupted cerebral perfusion during implantation, eliminates the need for deep hypothermic circulatory arrest and thoracotomy, reduces stroke risk, and provides an

innovative therapeutic alternative for patients.

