7.3. Caution

(1) Prior to using this device, physicians must receive specialized professional training and maintain a thorough understanding of the principles, clinical applications, complications, adverse reactions, and potential risks of aortic stent graft procedures.

(2) This procedure typically involves the combined use of one integrated ascending aortic stent graft, one integrated aortic arch segment stent graft, and three branched stent grafts. Implantation of an additional aortic extension stent graft may be determined based on the patient's vascular anatomy. To effectively prevent endoleak, appropriate specifications and models for the

integrated ascending aortic stent graft, integrated aortic arch segment stent graft, aortic extension stent graft, and branched stent grafts shall be selected preoperatively.

(3) During advancement and positioning of the integrated ascending aortic stent graft system, positioning shall be guided by the proximal and distal radiopaque markers on the main stent graft, as well as the radiopaque markers at the integrated branch regions, to align these markers with the predetermined optimal deployment position.

(4) During advancement and positioning of the branched stent graft systems for the innominate artery and left common carotid artery, the positional relationship between the proximal radiopaque markers and the proximal radiopaque rings of the integrated branches within the lumen of the main integrated ascending aortic stent graft shall be considered; meanwhile, the positioning of the distal radiopaque markers within the corresponding branch arteries shall be ensured.

(5) During advancement and positioning of the integrated aortic arch segment stent graft system, the positional relationship between its proximal radiopaque markers and the previously deployed proximal segments of the innominate and left common carotid branched stent grafts shall be considered; the fenestration radiopaque markers shall be aligned with the orifice of the left subclavian artery.

(6) During advancement and positioning of the branched stent graft system for the left subclavian artery, the positional relationship between its proximal radiopaque markers and the distal radiopaque rings of the integrated branches within the lumen of the main integrated aortic arch segment stent graft shall be considered; meanwhile, the positioning of the distal radiopaque markers within the left subclavian artery shall be ensured.

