8.1.7. Secondary Safety Endpoints

- (1) Rate of conversion to thoracotomy or secondary intervention. Whether subjects require

conversion to open thoracic surgery or secondary interventional procedures due to new-onset aortic dissection caused by the index procedure.

- (2) Rate of major adverse events occurring within 30 days after surgery. Refers to all-cause mortality, myocardial infarction, ischemic stroke or respiratory failure occurring within 30 days after surgery. More specifically, myocardial infarction refers to a drastic reduction or complete interruption of the coronary blood supply due to coronary artery disease, resulting in severe and prolonged acute ischemia of the corresponding myocardium, leading to necrosis of cardiomyocytes. Ischemic stroke refers to the end result of necrosis of brain tissue caused by narrowing or occlusion of the arteries supplying blood to the brain or insufficient blood supply to the brain. Respiratory failure is defined as a state resulting in significantly prolonged intubation, tracheotomy, deterioration of lung function, or other fatal outcomes.
- (3) Rate of aortic aneurysm-related mortality at 12 months post operation. Refers to mortality caused by a ruptured aortic aneurysm or endovascular interventional treatment.
- (4) Incidence of severe adverse events. Refers to an event that occurs during the clinical trial that results in mortality or serious deterioration in patient health, including a fatal illness or injury, a permanent defect in body structure or body function, or an event that requires medical or surgical intervention to avoid one or more permanent defects in body structure or body function.
- (5) Incidence of device-related adverse events. Device-related adverse events refer to an adverse medical event related to the use of a device that occurs during the course of the clinical trial. However, a distinction should be made with respect to normal postoperative stress response, such as fever and chest and back discomfort, which, in the judgment of the investigator, need not be recorded as an adverse event. Recording device-related adverse events will be applicable for conditions that are deemed by the investigator to be definitely related, possibly related, or of indeterminate relationship, to the test device.

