8.2.2. Trial Conduct

1) Visit 1: Screening Period (Day -15 to 0)

After the subject signs the informed consent form, baseline information and baseline examinations shall be collected, and screening shall be performed according to the inclusion and exclusion criteria. Eligible screened subjects will complete enrollment registration. The specific collected items are as follows:

- Demographic information, including age, gender, height, weight
- Physical examination data, including heart rate, respiration, blood pressure and body temperature
- Family history and previous medical history, including surgical history, concomitant diseases, concomitant medications and medical treatments
- Routine laboratory testing:
 - o Blood panel: Erythrocytes, leukocytes, platelet count and hemoglobin

- o Urine panel: pH, leukocytes, erythrocytes and proteins
- o Liver and kidney function: Creatinine, alanine aminotransferase (ALT), aspartate aminotransferase (AST), total bilirubin (TBIL) and direct bilirubin (DBIL)
- o Coagulation function: Activated partial thromboplastin time (APTT), prothrombin time (PT), internationalized standard ratio (INR), fibrinogen (FIB), thromboplastin time (TT) and D-dimer
- Pregnancy test (for female patients of childbearing age)
- Clinical Symptom Assessment (Modified Rankin Scale, mRS)
- 12-Lead ECG
- CTA angiography
- Cerebral CTA or MRA
- Echocardiography examination
- Concomitant medications

2) Visit 2: Intraoperative (0 day)

Record the procedural details; the specific collected items are as follows:

- Physical examination data
- DSA imaging data
- Surgery-related records (selection of stent type, arterial access, deployment, Interventional operation time (the time the sheath enters the body to the time the sheath is pulled out of the body), immediate success, etc.)
- Concomitant medications
- Adverse events
- Device defects

3) Visit 3: Before discharge

- Physical examination
- Blood panel: Erythrocytes, leukocytes, platelet count and hemoglobin
- Urine panel: pH, leukocytes, erythrocytes and proteins
- Liver and kidney function: Creatinine, alanine aminotransferase (ALT), aspartate

aminotransferase (AST), total bilirubin (TBIL) and direct bilirubin (DBIL)

- Coagulation function: Activated partial thromboplastin time (APTT), prothrombin time (PT), internationalized standard ratio (INR), fibrinogen (FIB), thromboplastin time (TT) and D-dimer
- Clinical Symptom Assessment (Modified Rankin Scale, mRS)
- 12-Lead ECG

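### Immediate technical success carries no condition on survival or open conversion, so a death or conversion during the index procedure can be scored as a success

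*Protocol*

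**What the plan says.** The synopsis (Secondary Efficacy Endpoints, item 1) and Section 8.1.6(1) give the same definition. It opens: "Immediate technical success is defined as successful delivery of the aortic and branching stent graft conveyors to their predetermined positions". It goes on to require "accurate positioning and successful deployment of the stent, safe removal of the delivery device outside the body", and closes with "absence of Type I and III endoleaks per imaging studies conducted at the end of the procedure with all branching stents patency". Nothing in either place refers to survival, to open conversion, or to which arch vessels must be perfused.

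Conversion has its own endpoint. Section 8.1.7(1) lists it under safety and asks whether subjects require "conversion to open thoracic surgery or secondary interventional procedures due to new-onset aortic dissection caused by the index procedure". Sections 4.2 and 8.1.2, by contrast, list conversion among the effectiveness endpoints and without the link to dissection.

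On the implant itself, Section 7.3(2) says that the usual set is "one integrated ascending aortic stent graft, one integrated aortic arch segment stent graft, and three branched stent grafts". Section 5 describes the system as reconstructing the innominate, left common carotid and left subclavian arteries, "achieving total endovascular repair without debranching surgery". Section 9.4.2(4) reports secondary efficacy endpoints as frequencies and percentages only.

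**The concern.** A technical success rate is normally read as the share of procedures that ended as intended. Here the definition stops at the state of the grafts. An operative death or an open conversion that follows a complete deployment and a clean angiogram changes none of its components. Sections 4.2 and 8.1.2 treat conversion as bearing on effectiveness, yet the procedural measure of effectiveness ignores it.

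The trial has a single arm and its 12-month results go to the regulator. With no control group built on the same definition, the percentage can be interpreted only through its wording. A reader of the report would not expect a procedure that ended in death or sternotomy to be among the successes.

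A smaller gap of the same kind lies in the patency component, which is asked of the branch stents and not of the arch vessels.

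**Working it through.** **1. Denominator.** Section 8.1.4.8 gives 72 valid cases and 20% dropout: 72 / (1 − 0.20) = 90, which reproduces the planned enrolment. Technical success is scored at implantation, so 90 is the natural denominator. The 72 is what should remain after later dropout.

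**2. Cases set against the definition.** The components are delivery; positioning and deployment; removal; no Type I or III endoleak on the completion image; branch stents patent.

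| Case during the index procedure | Components failed | Technical success as written | Counted in 8.1.7(1) |
|---|---|---|---|
| Death after full deployment, removal and clean imaging | none | success | no |
| Conversion for new-onset dissection, after the same | none | success | yes |
| Conversion for another cause (for example arterial perforation, listed in Section 14.4.3), after the same | none | success | no, on the plain reading |
| Conversion because a graft could not be delivered, deployed or withdrawn | delivery, deployment or removal | failure | no, on the plain reading |
| Planned branch graft not delivered or deployed | delivery or deployment | failure | not applicable |

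The first three rows are the gap. The last two show that the definition already catches many bad outcomes. The third row is the one that both measures can miss.

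**3. Effect on the rate.** If *m* subjects fall in the first three rows, the rate as written exceeds the rate under the stricter definition by *m*/90:

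- *m* = 0: 0 points
- *m* = 1: 1/90 = 1.1 points
- *m* = 2: 2/90 = 2.2 points
- *m* = 3: 3/90 = 3.3 points
- *m* = 5: 5/90 = 5.6 points

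The Protocol gives no figure from which *m* could be derived. The values above are illustrations, not estimates.

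**4. Patency component.** Section 5 and Section 6.1 name three vessels. Sections 7.3(4) and 7.3(6) give positioning instructions for all three branch grafts. The success definition names none of the vessels and sets no number of branches. Its wording therefore does not itself require what the device description promises, although a case that follows that description would have three stents to assess.

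**The case against.** The strongest reply is that a device-level success measure need not carry survival, because survival is measured elsewhere. That is largely true. An operative death counts in the primary endpoint (Section 8.1.5), in the 30-day major adverse events and among the serious adverse events (Section 8.1.7). A conversion would ordinarily surface as a serious adverse event too. No death is hidden, and no hypothesis test uses technical success. This limits the consequence but does not repair the definition, since the percentage will still be reported and read on its own.

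Three further points deserve weight.

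- Many conversions already fail another component. If the end of the procedure means the end of the whole operating session, a conversion that removes the graft may also fail on imaging. The Protocol does not say which moment is meant, and the synopsis places Visit 2 after completion of stent-graft deployment.
- The dissection qualifier in Section 8.1.7(1) could be read as attaching only to secondary interventions. All conversions would then be counted there. The plain reading attaches it to both.
- On patency, a reader might infer that a case planned with two branches and a covered or bypassed third vessel would pass as a full success. The documents describe no such procedure. The word typically in Section 7.3(2) is thin support, and Sections 5, 6.1 and 7.3 describe all three vessels being reconstructed. Section 8.1.6(5) also looks at branch vessel reconstruction at 1, 6 and 12 months. What stands is a wording gap, not a demonstrated route to false success.

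**Conclusion.** The point holds as a gap in a stated definition. As written, a subject who dies or is converted to open surgery during the index procedure, after complete deployment, device removal and clean completion imaging, is a technical success. A conversion not caused by new-onset dissection can also escape Section 8.1.7(1).

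The size is 1.1 percentage points per such subject, on 90 subjects. The number of subjects is not given and may be zero. A reader might infer that the rate is overstated, or that the bias runs to many points. The documents support neither: they give no rates of operative death or conversion, and any larger figure would also have to assume that every such case passes all the other components. The defensible statement is that the rate can be overstated.

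Nor should the endpoint's weight be exaggerated. It is secondary and descriptive, and it is not the only efficacy measure taken at implantation, because endoleak in Section 8.1.6(3) also has an intraoperative assessment. The comparison of the primary endpoint with the objective performance criterion (Section 9.4.2(3)) is untouched. This is a cheap improvement, not a threat to the trial's conclusion.

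**What to change.** Add one sentence to the definition in the synopsis and in Section 8.1.6(1): death or conversion to open surgery during the index procedure, from any cause, counts as technical failure.

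As a secondary clarification in the same two places, state the patency component in terms of the innominate, left common carotid and left subclavian arteries, each patent at the end of the procedure, instead of in terms of the branch stents placed.

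The surgical record and the intraoperative angiogram at Visit 2 already supply the data, so no new collection is needed. The cost is an amendment of two short passages and a reported success rate that may be slightly lower.
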